6.3.2. Examination of Subject Subsets

Subgroups defined by subject age group, (adolescent, 12 to <18 years; and adults, 18 to 65 years), geographic region (North America, Europe, Other), baseline HU use (yes, no), baseline VOC history (1, >1) will be analyzed to evaluate the internal consistency of the study outcomes. Subgroups defined by baseline Hb level will also be explored.

In addition, comparability of study cohorts (e.g., Group 1, Group 2a, Group 1 & 2a, and Group 2b) will be assessed. Specifically, descriptive statistics will be presented for each study cohort regarding the following:

- Demographics
- Baseline disease characteristics
- Subject disposition by study visit
- Rates of missing Hb assessment at Week 24

Hb response rate and Hb change from baseline in voxelotor treatment groups compared to placebo will also be summarized by study cohort.

6.3.3. Multiple Testing and Comparisons

A fixed sequence hierarchical test procedure will be used to formally evaluate voxelotor 1500 mg and 900 mg dose groups in comparison to placebo. The analysis will be based on data from the ITT population (i.e., all randomized subjects).

Interim Efficacy Analysis

Two interim analyses (IA) were to be performed to inform voxelotor dose selection. The first IA was performed with Group 1 data (n=62), followed by the second IA with the combined Groups 1 and 2a (n=156). The primary analysis will be performed based on data from all randomized subjects in Group 1 and Group 2 (n=274). A Lan-DeMets alpha spending function with the O'Brien-Fleming boundary is used to determine the significance level for each IA and the primary analysis, to maintain an overall type I error rate of 5% (two-sided), resulting in the following:

Analysis	Significance Level (two-sided)
IA #1 (n = 62)	0.000005
IA #2 (n = 156)	0.0059
Primary Analysis (n = 274)	0.0481

PASS Software (version 11) was used to calculate the alpha spending for each analysis (two-sample proportion).

Primary Efficacy Analysis

The first hypothesis testing will be to compare Hb response rate in voxelotor 1500 mg vs placebo. The test hypotheses are as follows:

$$H_0: p_v = p_c \quad \text{vs} \quad H_a: p_v \neq p_c$$

where p_v is the Hb response rate in voxelotor 1500 mg group and p_c is the Hb response rate in the placebo group.

The exact Cochran-Mantel-Haenszel (CMH) general association test, stratified by baseline HU use, age and geographic region, will be used for this analysis.

Secondary Efficacy Analyses

If the null hypothesis in the primary efficacy analysis is rejected at a two-sided significance level of 0.0481, the following hierarchically ordered statistical hypotheses will be tested in the order specified below, until the first non-rejection.

1. Change from baseline at Week 24 in Hb: voxelotor 1500 mg vs Placebo
2. Percent change from baseline at Week 24 in unconjugated bilirubin: voxelotor 1500 mg vs. Placebo
3. Percent change from baseline at Week 24 in reticulocyte %: voxelotor 1500 mg vs Placebo
4. Percent change from baseline at Week 24 in LDH: voxelotor 1500 mg vs Placebo
5. Hb response rate at Week 24 in Hb: voxelotor 900 mg vs Placebo
6. Change from baseline at Week 24 in Hb: voxelotor 900 mg vs Placebo
7. Percent change from baseline at Week 24 in unconjugated bilirubin: voxelotor 900 mg vs Placebo
8. Percent change from baseline at Week 24 in reticulocyte %: voxelotor 900 mg vs Placebo
9. Percent change from baseline at Week 24 in LDH: voxelotor 900 mg vs Placebo

6.3.4. Visit Windows

The blinded study period begins with the date of randomization, which is denoted in the protocol as Study Day 1. The conventions outlined below will be used to associate data measures, according to the study day corresponding to the date the data was collected, to an analysis visit window based on nominal (i.e., planned) visits, using the measure's study day relative to Day 1. Data collected before Study Day 1 will be considered screening information. Target study days, protocol acceptable ranges (per protocol) of study days for each scheduled assessment, and the analysis visit windows defined for each nominal visit day are shown in Tables 1 and 2.

If multiple assessments occur within a visit window, then the average of those assessments will be used for summarization and analysis.

Summarizations and analyses will utilize scheduled assessments and unscheduled assessments within a particular nominal window. Only central laboratory assessments will be included in summarizations and analyses of laboratory analytes.

Visit windows will be defined separately for non-PRO and PRO measures. PRO measures include ePRO Screening, ePRO SCD Severity Measure (SCDSM), eDiary data, EQ-5D-5L™, and CGI.

Table 1: Nominal Analysis Visit Windows for Non-PRO Measures

Nominal Visit Time	Target Study Day	Per Protocol Study Day Range	Study Day Range for Statistical Analysis*
Screening	-	[-35, -1]	[-35, -1]
Day 1	1	[-1, 1]	[-1, 1]
Week 2	14	[12, 16]	[2, 21]
Week 4	28	[26, 30]	[22, 35]
Week 6	42	[40, 44]	[36, 49]
Week 8	56	[54, 58]	[50, 70]
Week 12	84	[79, 89]	[71, 98]
Week 16	112	[107, 117]	[99, 126]
Week 20	140	[135, 145]	[127, 154]
Week 24	168	[163, 173]	[155, 210]
Week 36	252	[245, 259]	[211, 294]
Week 48	336	[329, 343]	[295, 378]
Week 60	420	[413, 427]	[379, 462]
Week 72	504	[497, 511]	[463, 545]

* Baseline is defined as the average of assessments on or prior the Study Day 1.

Table 2: Nominal Analysis Visit Windows for PRO Measures⁺

Nominal Visit Time	Study Day Range for Statistical Analysis[*]
Screening	[-35, -1]
Week 4	[1, 28]
Week 8	[29, 56]
Week 12	[57, 84]
Week 16	[85, 112]
Week 20	[113, 140]
Week 24	[141, 168]
Week 36	[169, 252]
Week 48	[253, 336]
Week 60	[337, 420]
Week 72	[421, 504]

* SCDSM scores on Study Days < -35 and Study Days > 168 will be excluded from SCDSM analyses

⁺ Notes:

(1) ePRO SCDSM is measured every day from the first day of Screening to Week 24 post randomization.

(2) EQ-5D-5L™ is administered at Day 1, Week 12 and then every 12 weeks while the subject remains on study. The final assessment of EQ-5D-5L™ will occur 4 weeks after the last dose of study drug. For the assessment of EQ-5D-5L™, Day 1 is defined as Baseline.

(3) The eDiary is triggered from Day 1 through EOS.

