4.10.1. Hematology

Hematology assessments will be performed through a central laboratory and will include the following:

- RBCs
- Hematocrit (Hct)
- Hemoglobin (Hb)
- Platelets
- White blood cells (WBCs) with differential (basophils, eosinophils, neutrophils, monocytes, and lymphocytes)
- % and absolute reticulocytes
- % dense cells (hyperchromic RBCs)
- RBC distribution width (RDW)
- Hb distribution width (HDW)
- Cell Hb concentration mean (CHCM)
- Mean corpuscular volume (MCV)
- Mean corpuscular hemoglobin concentration (MCHC)

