APPENDIX A. SCHEDULE OF ASSESSMENTS

Assessments	Screening	Treatment Period												Follow-Up EOS (last dose + 4 Wks)	
		D 1 ^a	W 2 ^b	W 4	W 6 ^b	W 8	W 12	W16 & W20	W 24	W 36	W 48	W 60	W72 ^c & EOT		
Study Day(s):	-35 to -1														
Informed Consent	X														
ePRO Screening (at least 28 days)	X														
Eligibility Assessment	X	x													
Medication and Medical History	X	x													
Physical Examination ^d	X	x	x	x	x	x	x	x	x	x	x	x	x	x	x
Height ^e	X								x		x		x		x
Weight	X						x		x	x	x	x	x		x
Randomization Assignment		x													
Vital Signs ^f	X	x	x	x	x	x	x	x	x	x	x	x	x	x	x
ECG ^g	X	x		x		x	x	x	x	x	x	x	x	x	x
ePRO SCDS Measure		x	x	x	x	x	x	x	x						
EQ-5D-5L ^{TM h}		x		x		x	x	x	x	x	x	x	x		x
Clinical Global Impression -Change (CGI-C; Groups 1 and 2 only)		x					x		x		x	x	x		
Adverse Events	X	x	x	x	x	x	x	x	x	x	x	x	x	x	x
Concomitant Medications		x	x	x	x	x	x	x	x	x	x	x	x	x	
eDiary		x	x	x	x	x	x	x	x	x	x	x	x	x	x
Hematology ⁱ	X	x	x	x	x	x	x	x	x	x	x	x	x	x	x
Erythropoietin		x					x		x	x	x	x	x		x
Exploratory Assessments ^j		x					x		x	x	x	x	x		x
HbF analysis		x					x		x				x		x
Blood Sample for Pharmacogenomic Analysis (if participant opted in on ICF)		x													
Serum Chemistry ^k	X	x	x	x	x	x	x	x	x	x	x	x	x	x	x
Urinalysis ^l	X														x

Assessments	Screening	Treatment Period													Follow-Up EOS (last dose + 4 Wks)
		D 1 ^a	W 2 ^b	W 4	W 6 ^b	W 8	W 12	W16 & W20	W 24	W 36	W 48	W 60	W72 ^c & EOT		
Study Day(s):	-35 to -1														
Coagulation ^m	X														
Serum Pregnancy Test ⁿ	X														
Urine Pregnancy Test ⁿ		x		x		x	x	x	x	x	x	x	x		x
Serum Virology ^o	X														
Iron Studies ^p	X														
Pharmacokinetic Sampling			x ^q				x ^q	x ^q		x	x	x	x	x	

Abbreviations: D = day; ECG = electrocardiogram; EOS = End of Study; EOT = End of Treatment; ePRO = electronic patient reported outcomes; EQ-5D-5L™ = EuroQol EQ-5D-5L™ health questionnaire; HbF = hemoglobin fetal; ICF = informed consent form; SCDS = sickle cell disease severity; W = week; Wks = weeks.

Note: Study visits must be conducted within ± 2 days of the scheduled visit through Week 8, and ± 5 days through Week 24, and ± 7 days for the subsequent visits through EOT; the EOS visit should be completed at 4 weeks (± 7 days) after last dose of study drug.

- a Day 1 assessments should be performed at least 30 minutes prior to study drug administration and may be performed on Day -1.

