Hemoglobin (Hb) response is based on the difference between the average value of Hb levels at Week 20 (Hb20) and Week 24 (Hb24) and baseline Hb level (HbB). A subject is considered to be a Hb responder if $[\text{mean}(\text{Hb20}, \text{Hb24}) - \text{HbB}] > 1 \text{ g/dL}$. If Hb20 or Hb24 is missing, then the calculation will use the non-missing Hb level. Regardless of calculated difference, subjects will be classified as a non-responder if any of the non-responder criteria in [Section 6.3.5.1](#) are met.

Hemoglobin Worsening at Week 24

- Severe anemic episode - worst Hb between weeks 12 and 24 inclusive is $< 5.5 \text{ g/dL}$
- Acute anemic episode - worst Hb between weeks 12 and 24 inclusive, is $\geq 5.5 \text{ g/dL}$ and $< 7 \text{ g/dL}$

Rate of Opioid Use During Treatment Period

The rate of opioid use is calculated as the number of days opioids were taken for SCD symptom management (as recorded in the eDiary) divided by the number of days with non-missing eDiary data from date of randomization to date of last dose.

Total Symptom Score (TSS)

For each subject, the TSS will be computed as follows: The Baseline TSS is the average of the scores during the 28 to 35-day Screening period. Similarly, post randomization when there is at least 75% compliance during a 4-week period, the TSS is the average score for each 4-week period. The 4-week periods are Weeks 1-4 (Study Day 1-28), Weeks 5-8 (Study Day 29-56), and Weeks 9-12 (Study Day 57-84) and follows similarly for subjects whose involvement exceeds 12 weeks up to Week 24. If there is a delay in initiating study treatment, all TSS data prior to administering treatment will be included with the Screening period data. All TSS data post dose through Study Day 28 will constitute Weeks 1-4. If missing data in a 4-week period is due to lack of compliance or subject dropout, the TSS will be set to missing for the 4-week period. Missing data due to VOC, VOC hospitalization or RBC transfusion will be imputed as described

in Section 6.3.5. Compliance of at least 60% during each 4-week period will also be examined in a sensitivity analysis for TSS.

TSS₁₀₀ is TSS rescaled from a 27-point scale to 100-point scale. Algebraically, this is accomplished as follows:

$$TSS_{100} = TSS \times \frac{100}{27}.$$

Clinical Global Impression of Change

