6.3.5.1. Hemoglobin Responder

- If Hb assessment is missed at both Week 20 and Week 24 due to dropout, VOC, or VOC hospitalization: Subject will be treated as a non-responder. If Hb at one of the two time points is non-missing, Hb response assessment will be based on the non-missing Hb value.
- Initiation of HU post randomization and prior to Week 24: Subject will be treated as a non-responder.

[figure not shown]
- RBC transfusions: A participant who receives a transfusion due to anemia within 8 weeks (12 weeks for sensitivity analysis) of the Week 24 Hb assessment will be deemed a non-responder. For subjects receiving transfusion due to reasons other than anemia within 8 weeks (12 weeks for sensitivity analysis) of the Week 24 Hb assessment, Week 24 Hb will be imputed with the last Hb assessment prior to the transfusion.

Example: In Figure 1, an RBC transfusion due to anemia occurred at Day 114. If the Week 24 Hb assessment occurs before Day 170 then the participant will be deemed a non-responder; otherwise the Week 24 Hb measure will then be compared to Baseline to determine whether the participant meets the definition of responder (i.e. $8.1 - 7.95 = 0.15$, which is classified as a non-responder). If the RBC transfusion is not due to anemia, then the Hb assessment prior to Day 114 (i.e., the Week 12 assessment, which is 7.0 g/dL) will be used for imputation of Hb for assessments occurring from Study Day 114 to Study Day 170 (8-week imputation) or to Study Day 198 (12-week imputation). The Week 24 Hb measure will then be compared to Baseline to determine whether the participant meets the definition of responder.

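### The Week 24 averaging rule mixes an off-drug End of Study hemoglobin into Hb24 for subjects who are sampled on drug at Week 24 and stop at about Days 163-182

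*SAP*

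**What the plan says.** **Windowing (SAP 6.3.4).** A sample is assigned "according to the study day corresponding to the date the data was collected, to an analysis visit window", so its visit label on the case report form does not decide where it goes. Both planned and extra draws count: "Summarizations and analyses will utilize scheduled assessments and unscheduled assessments within a particular nominal window." The one filter on source is: "Only central laboratory assessments will be included in summarizations and analyses of laboratory analytes." Several values in one window are combined: "If multiple assessments occur within a visit window, then the average of those assessments will be used for summarization and analysis."

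**Window limits (SAP Table 1).** Week 24 has target Day 168, a per-protocol range of Days 163-173 and an analysis range of Days 155-210. The table has no row for EOS or End of Treatment.

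**EOS sample (Protocol Appendix A).** The last column is headed "Follow-Up EOS (last dose + 4 Wks)" and hematology is marked there. A note to the schedule allows 7 days either side. Protocol 4.10.1 makes this a central test: "Hematology assessments will be performed through a central laboratory and will include the following." An EOS hemoglobin therefore passes the central-laboratory filter.

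**Primary value (SAP 4).** Hb response "is based on the difference between the average value of Hb levels at Week 20" and Week 24, and the baseline level. The threshold is a rise of more than 1 g/dL. If one of the two values is missing, the other is used alone.

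**Transfusion rule (SAP 6.3.5.1).** A subject transfused for anemia "within 8 weeks (12 weeks for sensitivity analysis) of the Week 24 Hb assessment" is a non-responder.

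**The concern.** The schedule places EOS four weeks after the last dose, so its hemoglobin is an off-drug value. If treatment ends shortly after the Week 24 visit, that value still falls before Day 211. The rule then averages it with the on-drug Week 24 sample, and the result goes into the primary endpoint and the Week 24 hemoglobin change, which is the first secondary test. Table 1 covers all non-PRO measures, so the Week 24 hemolysis measures follow the same rule.

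A drug effect can be lost only in the voxelotor arms, so any dilution falls on those arms alone.

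The transfusion rule has a separate difficulty, in any arm. It is anchored to the date of a single Week 24 assessment. When Hb24 is an average of samples from different days, no such single date exists.

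**Working it through.** **1. The plan's own figure.** SAP 6.1 gives >95% power for 40% against 10% response, about 90 per arm, Fisher's exact test, two-sided alpha 0.0481. Enumerating all 2x2 tables for 90 per arm gives 99.7%, so the statement is reproduced.

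**2. Who is affected.** Nominal EOS day = last-dose day + 28.

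- EOS falls in Days 155-210 when the last dose is on Days 155 - 28 = 127 to 210 - 28 = 182.
- An on-drug Week 24 sample is diluted only if the last dose comes on or after that sample. The sample is due on Days 163-173, so the relevant last doses are about Days 163-182, with nominal EOS on Days 191-210.
- With the 7-day allowance, a last dose on Day 163 gives EOS on Days 184-198, and one on Day 175 gives Days 196-210, both wholly inside the window. From Day 176 to Day 189 inclusion depends on the actual EOS date.
- A last dose on Day 168, the 24-week minimum in Appendix A footnote c, gives EOS on Day 196 (189-203), inside the window. A last dose on Day 504 (Week 72) gives Day 532, far outside it.

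**3. Weight of the EOS value.** Let d be the on-drug rise, the same at Weeks 20 and 24, and r the fraction of d still present at EOS. The documents do not give r.

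- Week 24 change = (d + rd)/2
- Primary value = [d + (d + rd)/2]/2 = d(0.75 + 0.25r)
- Rise needed to respond: d > 1/(0.75 + 0.25r)
- If Hb20 is missing: d > 1/(0.5 + 0.5r)

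| Assumed loss by EOS | Week 24 change | Primary value | Rise needed (g/dL) | Rise needed, Hb20 missing |
|---|---|---|---|---|
| None (r = 1) | d | d | >1.00 | >1.00 |
| Half (r = 0.5) | 0.75d | 0.875d | >1.14 | >1.33 |
| Full (r = 0) | 0.5d | 0.75d | >1.33 | >2.00 |

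Example: a rise of 1.3 g/dL with full loss gives 0.75 x 1.3 = 0.975, so a responder becomes a non-responder. If a separate End of Treatment sample also lies in the window and is on drug, EOS has weight 1/6 and the full-loss threshold is 1/(5/6) = 1.20.

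**4. Effect on the arm.** The affected share f of the 1500 mg arm is not given, so this is an illustration. Assume normal on-drug changes with SD 0.6 g/dL (the Group 1 planning value in Protocol 8.2.1) and mean 1 - 0.2533 x 0.6 = 0.848, which gives 40% responders. Placebo stays at 10%. Among affected subjects the response rate becomes:

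- full loss: P(Z > (1.333 - 0.848)/0.6) = 20.9%
- half loss: P(Z > (1.143 - 0.848)/0.6) = 31.2%

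Arm rate = 0.40(1 - f) + f x affected rate.

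| f | Full loss: rate, power | Half loss: rate, power |
|---|---|---|
| 5% | 39.1%, 99.6% | 39.6%, 99.7% |
| 10% | 38.1%, 99.4% | 39.1%, 99.6% |
| 20% | 36.2%, 98.7% | 38.2%, 99.4% |

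**5. Transfusion date.** The SAP's own example has an anemia transfusion on Day 114, so the 8-week limit is Day 114 + 56 = 170. With samples on Days 168 and 196, the first date makes the subject a non-responder and the second sends the subject to the measured value. For an anemia transfusion on Day 180, the Day 168 sample precedes it and the Day 196 sample follows it by 16 days, so classification again depends on which date is used.

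**The case against.** **Off-drug values belong in this trial.** Efficacy is analyzed by ITT (SAP 7.1), and subjects are followed through the primary efficacy period even after stopping drug (Protocol 2.1.6, 4.14.2.1). This stands, and it limits the point. A reader might infer that every subject with a last dose on Days 127-182 has a diluted endpoint. The documents do not support that. For last doses on about Days 127-162 the scheduled Week 24 sample is itself off drug, so no on-drug Hb24 is diluted. For Days 127-139 the nominal EOS sample (Days 155-167) precedes Day 168 and is closer to the last dose, so including it could even raise Hb24.

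**Few subjects, and no threat to the conclusion.** Treatment may run to Week 72, expected dropout is below 10% (Protocol 8.4.2), and only part of it could fall in a 20-day span. This also stands. The transfusion and hydroxyurea rules further override the average for some subjects.

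**The text may already settle it.** SAP 8.2.1.1 confines the primary analysis to data through Week 24, but it sets no day limit, and Table 1 lets Week 24 run to Day 210. SAP Section 14 (programming specifications) cannot be read in the public copy. If it holds a rule, that rule should be stated in 6.3.4.

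**Transfusion imputation works by date.** For transfusions not due to anemia, the SAP example imputes each assessment by its own day, so no ambiguity arises. It remains only for the anemia non-responder rule.

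**Averaging is a prespecified choice, in keeping with averaged baselines.** This is fair for repeat on-drug samples. It gives no reason to combine an on-drug sample with one taken four weeks after the last dose.

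**Conclusion.** The point holds for an identifiable group: subjects with an on-drug scheduled Week 24 sample and a last dose on about Days 163-182. For them EOS supplies one quarter of the primary value when Hb20 is present. The rise needed to respond goes from >1.00 to >1.33 g/dL under full loss of the gain, or >1.14 under half loss. The Week 24 change entering the MMRM is halved under full loss. Both degrees of loss are assumptions, as is one on-drug sample plus one EOS sample in the window.

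The number affected is not given and is probably small. The dilution works against voxelotor. A reader might infer that the primary test is endangered. It is not: power is still 98.7% with 20% of the 1500 mg arm affected and full loss. The anemia-transfusion ambiguity is separate, needs no assumption about loss of effect, and can arise in any arm. This is a gap in the endpoint definition that is cheap to close.

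**What to change.** Amend SAP 6.3.4 before Group 2b is unblinded:

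1. Do not map an EOS sample to a visit window that already holds a scheduled sample for that visit.
2. Use the scheduled Week 24 sample as Hb24. If it is missing, use the in-window sample nearest Day 168.
3. State in 6.3.4, with a cross-reference in 6.3.5.1, that this sample's date is the Week 24 assessment date for the transfusion rule.
4. Keep the all-sample average as a sensitivity analysis.

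**Cost.** The change is wording and a small derivation edit. Values become slightly noisier for the few subjects with repeat on-drug samples. If the scheduled sample is missing, EOS may still supply the whole of Hb24. That can already happen under the current rule, and it fits follow-up after stopping drug.

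The main cost is timing. Data from 156 of 274 subjects have been unblinded, including to sponsor biostatistics and programming staff (SAP 2, 6.2), and the change would tend to favor voxelotor. The SAP should record that it was made without reference to unblinded data.

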4.12. EuroQol EQ-5D-5L Health Questionnaire

EQ-5D-5L™ is a standardized instrument for use as a measure of health outcome. EQ-5D-5L™ is applicable to a wide range of health conditions and treatments, and it provides a simple descriptive profile and a single index value for health status. Participants will complete the EQ-5D-5L™ at the start of the defined clinic visits using the handheld study-specific device.

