The Clinical Global Impression of Change (CGIC) is a 7-point scale that requires study medical personnel to assess clinically meaningful change in a participant's sickle cell disease. The rating scale is as follows:

- Very much improved
- Moderately improved
- Minimally improved
- No change
- Minimally worse
- Moderately worse
- Very much worse

CGIC is assessed at Week 24, Week 48, End of Treatment (EOT), and End of Study (EOS).

Incidences of VOC, RBC Transfusion, ACS or Pneumonia On Study

Cumulative incidences of each named event is defined as the number of events from date of randomization to end of study, inclusive.

Time (in weeks) to First VOC

Time to first VOC during the study is defined as

$$(\text{Date of First VOC On Study} - \text{Date of Randomization} + 1) / 7.$$

Subjects who do not have a VOC will be censored at the end of study.

Time (in weeks) to First RBC Transfusions

Time to first RBC transfusions during the study is defined as

$$(\text{Date of First RBC transfusion On Study} - \text{Date of Randomization} + 1) / 7.$$

Subjects who do not have an RBC transfusion will be censored at the end of study.

Time (in weeks) to First ACS or Pneumonia

Time to first ACS or Pneumonia during the study is defined as

$$(\text{Date of First ACS or Pneumonia On Study} - \text{Date of Randomization} + 1) / 7.$$

Subjects who do not have an ACS or pneumonia will be censored at the end of study.

Adverse Event

An AE is defined as any untoward medical occurrence in a subject administered a pharmaceutical product during the course of a clinical investigation. For greater details, refer to Protocol Section 9.1.1.

All adverse events will be recorded on the Adverse Event CRF.

For this study's definition of a Serious Adverse Event (SAE), please refer to Protocol Section 9.1.2.

Treatment-emergent Adverse Event

A treatment-emergent adverse event (TEAE) is defined as an AE that emerges on or after initiation of study drug (having been absent pre-treatment), or an AE that existed pre-treatment and worsened on treatment (relative to the pre-treatment state) through 28 days after study drug discontinuation.

Treatment-emergent Laboratory Abnormalities

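### The SAP's PRO visit windows end on the target day, so EQ-5D-5L and CGI assessments made late but within tolerance are reported under the next window, and late Week 72 assessments have no window

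*SAP*

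**What the plan says.** SAP Section 6.3.4 sets up two window tables: "Visit windows will be defined separately for non-PRO and PRO measures. PRO measures include ePRO Screening, ePRO SCD Severity Measure (SCDSM), eDiary data". The same sentence then adds EQ-5D-5L and CGI to the PRO list. Table 2 holds the PRO windows, and Table 1 holds those for all other measures.

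Data are assigned "according to the study day corresponding to the date the data was collected". Where a window holds more than one value, the SAP says: "If multiple assessments occur within a visit window, then the average of those assessments will be used for summarization and analysis".

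Each post-baseline window in Table 2 closes on the target day given in Table 1: Week 24 is [141, 168] with target Day 168, and Week 72 is [421, 504] with target Day 504. Table 1 also gives the permitted visit ranges, such as [163, 173] for Week 24. They match the tolerance in Protocol Section 4 and Appendix A: ±2 days through Week 8, ±5 through Week 24 and ±7 afterwards.

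Neither instrument is a daily measure. Protocol Section 4.12 has participants complete EQ-5D-5L "at the start of the defined clinic visits using the handheld study-specific device". Note 2 to Table 2 says that it "is administered at Day 1, Week 12 and then every 12 weeks while the subject remains on study", with a last assessment that "will occur 4 weeks after the last dose of study drug". Protocol Appendix A has a fuller EQ-5D-5L schedule that adds Weeks 4, 8, 16 and 20. For CGI, SAP Section 4 lists Weeks 24 and 48, end of treatment and end of study, whereas Appendix A marks Day 1 and Weeks 12, 24, 48, 60 and 72/EOT.

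**The concern.** A block that closes on the target day is right for SCDSM and eDiary entries, which accumulate daily up to that day. For an assessment made once, at a clinic visit, it leaves no room for a visit after the target day, although the protocol allows one.

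As written, a late compliant value has one of three fates:

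- **Wrong label.** A late Week 24 CGI rating is reported at Week 36, where neither document schedules CGI. On the SAP schedule, a late Week 12 EQ-5D-5L value is reported at Week 16, where none is planned.
- **Mixing.** A Week 24 EQ-5D-5L value on Day 170 and an on-time Week 36 value on Day 250 are averaged and reported as Week 36. Week 24 then has no value for that patient, unless a late Week 20 value (Appendix A schedule) has moved into it. On the Appendix A schedule, a late Week 48 CGI rating shares a window with an on-time Week 60 rating.
- **Loss.** A late Week 72 value belongs to no window.

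At stake is whether the by-visit EQ-5D-5L and CGI summaries, including those at Weeks 24 and 72, describe the visits they are labelled with.

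**Working it through.** **Inputs.** Target days, permitted ranges and both sets of analysis windows come from SAP Section 6.3.4, Tables 1 and 2. The tolerances come from Protocol Section 4.

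**Reproducing the plan's own figures.** Target = 7 × week; permitted range = target ± tolerance. For Week 24: 7 × 24 = 168 and 168 ± 5 = [163, 173]. For Week 72: 7 × 72 = 504 and 504 ± 7 = [497, 511]. All twelve post-Day 1 rows of Table 1 reproduce exactly.

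**Mapping each permitted day to Table 2.**

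| Visit | Permitted days | Table 2 window | Days in own window | Days outside it | Where they go |
|---|---|---|---|---|---|
| Week 4 | 26–30 | [1, 28] | 3 | 2 (29–30) | Week 8 |
| Week 8 | 54–58 | [29, 56] | 3 | 2 (57–58) | Week 12 |
| Week 12 | 79–89 | [57, 84] | 6 | 5 (85–89) | Week 16 |
| Week 16 | 107–117 | [85, 112] | 6 | 5 (113–117) | Week 20 |
| Week 20 | 135–145 | [113, 140] | 6 | 5 (141–145) | Week 24 |
| Week 24 | 163–173 | [141, 168] | 6 | 5 (169–173) | Week 36 |
| Week 36 | 245–259 | [169, 252] | 8 | 7 (253–259) | Week 48 |
| Week 48 | 329–343 | [253, 336] | 8 | 7 (337–343) | Week 60 |
| Week 60 | 413–427 | [337, 420] | 8 | 7 (421–427) | Week 72 |
| Week 72 | 497–511 | [421, 504] | 8 | 7 (505–511) | no window |

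**Totals.** Misplaced days: 2×2 + 4×5 + 4×7 = 52. Permitted days: 2×5 + 4×11 + 4×15 = 114. So 52/114 = 46%. Under the Table 1 analysis windows (for example Week 24 [155, 210] and Week 72 [463, 545]) the count is 0 of 114.

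The ten-visit total applies to EQ-5D-5L on the Appendix A schedule. By SAP schedule:

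- EQ-5D-5L (Weeks 12, 24, 36, 48, 60, 72): 2×5 + 4×7 = 38 of 2×11 + 4×15 = 82 days, or 46%.
- CGI at its two fixed weeks (24 and 48): 5 + 7 = 12 of 11 + 15 = 26 days, or 46%.

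**End-of-study assessment** (last dose + 28 days, ± 7). A last dose on Day 504 gives Days 525–539, in no Table 2 window but inside Table 1 Week 72. A last dose on Day 168 gives Days 189–203, inside Table 2 Week 36 and Table 1 Week 24. Under either table an off-treatment value can be missed or counted as an on-treatment visit.

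**Patients affected.** The documents give no visit dates, so this cannot be computed. For illustration, suppose all 274 randomised subjects were assessed at Week 24 and a given share came late within tolerance: 274 × 5% = 13.7, 274 × 10% = 27.4 and 274 × 25% = 68.5, or about 14, 27 and 68 subjects.

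**The case against.** The best defence is that little depends on it. SAP Section 8.2.3.2 says only that these measures are summarised descriptively, and no visible sentence specifies the by-visit tables. The output lists and programming specifications are redacted and might handle late visits. That cannot be excluded. But windows exist in order to produce by-visit summaries, and no visible text corrects the rule. The SAP Section 4 definition of a study visit as the nominal CRF visit does not help, because Section 6.3.4 assigns data by study day. The exclusion of days after 168 covers SCDSM only, and note 2 gives a schedule and a baseline but no windows.

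Several narrower points stand as limits on size:

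- CGIC has seven verbal categories, so the averaging rule has no clear meaning for it. That is a further reason not to apply the rule to CGI.
- The subject counts are upper limits: Appendix A makes EQ-5D-5L available country by country, and some subjects discontinue.
- At the data cutoff only 24 weeks of follow-up is assured (SAP Section 2), so the late-visit problem from Week 48 to Week 72 concerns a subset in this analysis.

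**Conclusion.** The concern holds and is minor. Followed as written, Section 6.3.4 moves every EQ-5D-5L or CGI assessment made after the target day but within tolerance into the next window and, at Week 72, into none. That is 2 of 5 permitted days at Weeks 4 and 8, 5 of 11 at Weeks 12 to 24, and 7 of 15 from Week 36 on. On-target and early visits are placed correctly, so the share of patients affected at a visit equals the share seen late within tolerance, which the documents do not give.

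The effect is confined to exploratory, descriptive summaries. The same windows apply in all arms. The haemoglobin endpoint and the fixed-sequence tests use laboratory data under Table 1 and are untouched. The conclusion rests on the visible SAP text being the operative rule.

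**What to change.** Amend SAP Section 6.3.4 in four places:

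1. Restrict Table 2 to the daily electronic data: SCDSM, including its screening entries, and eDiary.
2. Assign EQ-5D-5L and CGI by the Table 1 analysis windows, for example Week 24 = Days 155–210. This also stops the Day 1 EQ-5D-5L baseline from falling in the Week 4 window [1, 28].
3. Where several EQ-5D-5L or CGI values fall in one window, use the scheduled assessment nearest the target day, not the average.
4. Summarise the end-of-study assessment as its own time point, so that it enters neither the Week 72 window [463, 545] nor any other on-treatment window.

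The cost is a short SAP edit and a small programming change. No new data are needed.
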